#### General study level definitions 3.2

#### 3.2.1 **Relative day**

Relative day will be calculated as the current date minus the date of first dose of study drug administration plus 1 for days on or after the day of first dose of study drug dose. Relative day 1 is the date of first bimekizumab administration.

3001

Relative days before first administration of bimekizumab will have the prefix "-" and will be calculated as date of first dose of study drug administration minus the current date.

For days after the last bimekizumab administration, relative day will be calculated as the current date minus the date of last dose of study drug administration including the prefix "+".

Calculations of "Relative Day" should not include partial dates, but should be left blank in these instances.

For AEs, relative days for start and stop dates will be calculated as the number of days since the first injection of the medication. For non-treatment emergent AEs, relative day of onset will be negative if the event started and stopped before the first dose. A complete date must be established in order to correctly identify the AEs. Section 4.2.2 describes imputation rules in case of missing data for AEs.

### 3.2.2 **Study Periods**

The following study periods are defined for the classification by study period:

- Pre-treatment period (Screening period): up to 28 days, ends with the visit date of the first dose of study medication (Visit 2)
- Double-Blind treatment period: starts with the visit date of the first dose of study medication (Visit 2), ends at Week 12 visit date

his docu

- Dose-Blind treatment period: starts at the Week 12 visit, ends at Week 48 visit
- Post-treatment period: the post-treatment period (Follow-up period) is the period after the Week 48 visit

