#### 10.2 Adverse events (AEs)

An AE is any untoward medical occurrence in a patient or clinical investigation subject administered a pharmaceutical product that does not necessarily have a causal relationship with this treatment. An AE can therefore be any unfavorable and unintended sign (including an abnormal laboratory finding), symptom, or disease temporally associated with the use of a medicinal (investigational) product, whether or not related to the medicinal (investigational) product.

AEs (including serious AEs) are characterized as either non-treatment or treatment emergent according to the following criteria:

- Non-treatment emergent are the events with onset date and time prior to the very first administration of study medication (bimekizumab or placebo) or after a 140-day period after the final drug administration.
- Treatment-emergent AEs (TEAE) are those with onset date at or after the very first administration of study medication. The events that emerge within 140 days after the final drug administration, will also be considered as treatment emergent (eg, in the case of premature discontinuation or during the SFU period).

All AEs occurring during the study (i.e., after signature of the informed consent document) will be recorded in the eCRF. For each AE the following information will be recorded in the eCRF: AE term (verbatim term), date of onset, whether or not the AE was classified as a SAE, as an AE of special interest, intensity, relationship to study medication, action taken with study medication, other action taken, outcome, date of outcome, and whether the AE led to study drug discontinuation or to study discontinuation.

ADRs are defined as a response to a drug which is noxious and unintended and which occurs at doses normally used in man for prophylaxis, diagnosis, or therapy of disease or for modification of physiological function. Any AE that is considered "Related" to study treatment will be classed as an ADR.

If an AE occurs on the same day as the treatment switch (Visit 7, Week 12) then the AE will be allocated to the Double-Blind treatment. An exception from this general rule is made for adverse drug reactions (ADRs), and AE of hypersensitivity reactions and anaphylactic reactions. If those AEs occur on the same days as the treatment switch, the AEs will be allocated to the Dose-Blind treatment.

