## **Clinical laboratory evaluations**

his docurr The routine clinical laboratory evaluations specified in Table 10-1 and will be summarized. If any additional analytes are also recorded then these will be listed only.

Different summary tables for hematology and biochemistry variables will be provided, based on data from scheduled visits: observed values and change from Baseline, shift from Baseline to

maximum post-Baseline value (in Double-Blind Period), shift from Baseline to maximum post-Baseline value (in Dose-Blind Period), shift from Baseline to minimum post-Baseline value (in Double-Blind Period), shift from Baseline to minimum post-Baseline value (in Dose-Blind

Linu of treatment (in Double-Blind Period) will be defined as the last visit in the Double-Blind Period or the early termination assessment depending if the subject discontinued in the Double-Blind Blind Period.

End of treatment (in Dose-Blind Period) will be defined as the Week 48 visit or the early of termination assessment depending if the subject discontinue 1

In addition, number of subjects who meet the Hy's Law criteria (Section 10.2) will be described using frequencies.

All laboratory data will be listed by treatment, subject and visit including changes from Baseline for numeric variables, flags for measurements outside the normal ranges, the relative study day, a flag for whether the test was not done and a flag for whether the subject was fasting.

Additional listings will be presented for Hepatitis B and C, human immunodeficiency virus (HIV), genomic proteomic/metabolomics, and genetic/epigenetic tests. CRP and hs-CRP will be tabulated and listed separately in the efficacy section

Hematology	Biochemistry	Urinalysis
Basophils	Biochemistry C Hot Calcium	Bacteria
Eosinophils	Chloride	Crystals
Lymphocytes	Magnesium	Glucose
Monocytes	Potassium	pH
Neutrophils	Sodium	RBC
Hematocrit	Glucose	WBC
Hemoglobin	BUN	Urine dipstick for pregnancy testing
MCH god	Creatinine	
MCHC C	AST	
MCV ot	ALT	
Platelet count	ALP	
RBC count	GGT	
WBC count	Total bilirubin	
WBC count	LDH	
	Uric acid	
	Total cholesterol	

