### Has been changed to

. . .

variations thereof. Different summary tables for hematology and biochemistry variables will be provided, based on data from scheduled visits: observed values and change from Baseline, shift from Baseline to maximum post-Baseline value (in Double-Blind Period), shift from Baseline to maximum post-Baseline value (in Dose-Blind Period), shift from Baseline to minimum post-Baseline value (in Double-Blind Period), shift from Baseline to minimum post-Baseline value (in Dose-Blind Period), shift from Baseline to end of treatment (in Double-Blind Period), shift from Baseline to end of treatment (in Dose-Blind Period), and markedly abnormal laboratory data.

End of treatment (in Double-Blind Period) will be defined as the last visit in the Double-Blind Period or the early termination assessment depending if the subject discontinued in the Double-Blind Period.

End of treatment (in Dose-Blind Period) will be defined as the Week 48 visit or the early termination assessment depending if the subject discontinued early or not.

... Table 10-5 updated to align with Table 12-4 from the Protocol Amendment 2. This document cannot be used to support any many

The formation of the seaf of t

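### The Week 12 visit falls in both treatment periods, so Week 12 laboratory values can enter the Dose-Blind maximum/minimum shift tables although they reflect the earlier treatment

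*SAP*

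**What the plan says.** Section 3.2.2 defines the periods used for classification. The Double-Blind Period "starts with the visit date of the first dose of study medication (Visit 2), ends at Week 12 visit date". The next line reads "Dose-Blind treatment period: starts at the Week 12 visit, ends at Week 48 visit". Neither line refers to dosing or re-randomization.

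Section 10.3 uses these periods for haematology and biochemistry. From scheduled visits it plans shift tables to the highest and to the lowest later value, each produced once per period. The list contains, for example, "maximum post-Baseline value (in Double-Blind Period), shift from Baseline to maximum post"; the Dose-Blind and minimum versions come next in the same list. The Double-Blind end-of-treatment value comes from the last visit of that period, or from the early termination assessment.

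Section 10.2 has a switch-day rule, limited to adverse events. It opens with the words "If an AE occurs on the same day as the treatment switch (Visit 7, Week 12) then the AE will be" and assigns such events to the Double-Blind treatment. Adverse drug reactions, hypersensitivity and anaphylactic reactions are excepted and go to the Dose-Blind treatment.

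Section 2.3 keeps the 160 mg and 320 mg arms on their dose and re-randomizes the placebo, 16 mg and 64 mg arms to 160 mg or 320 mg at Week 12. Section 4.3.1 puts the last Double-Blind dose at Week 8, so the Week 12 injection is the first Dose-Blind dose.

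**The concern.** One scheduled laboratory result qualifies for two sets of worst-value tables. For a completer, Week 12 is the last Double-Blind visit and so gives the Double-Blind end-of-treatment value. By Section 3.2.2 it is also the first Dose-Blind value. If a subject's highest ALT or lowest neutrophil count from Week 12 onward occurs at Week 12, the Dose-Blind table reports it as a Dose-Blind extreme, although the preceding 12 weeks were on placebo or a lower dose.

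The Dose-Blind tables should describe laboratory safety on 160 mg and 320 mg, and they would be mixed with values from before the switch. Two programmers could also follow this text and produce different tables, depending on how each sets the period flag at Week 12. Adverse event and laboratory outputs could then treat the same visit differently.

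**Working it through.** The SAP gives no figure to reproduce here. The check compares the definitions and then gauges the scale.

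**Which rules decide the period of a Week 12 result**

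- Section 3.2.2: both periods include the Week 12 visit.
- Section 3.3: its same-day timing rule concerns Baseline and the first administration at Visit 2, not Week 12.
- Section 10.1: exposure and time at risk for subjects who continue are cut at the first Dose-Blind injection. This covers person-time, not laboratory values.
- Section 10.2: the switch-day rule covers adverse events only.
- Section 10.3: it uses the periods but does not say which one owns Week 12 for the maximum and minimum.

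No rule removes the Week 12 result from the Dose-Blind tables.

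**Who can be affected**

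Section 2.4 plans 5 × 57 = 285 subjects. Three arms switch: 3 × 57 = 171, and 171/285 = 60%. This is an upper limit, because subjects who leave before Week 12 do not enter the Dose-Blind Period. The other two arms keep their dose, so for them the value is only counted twice.

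**How many shift categories could change**

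A shift category gets worse only if the Week 12 result is abnormal in the given direction and all later Dose-Blind results are not. The inputs below are assumptions, since the SAP contains neither the laboratory schedule nor abnormality rates: K laboratory visits after Week 12, and probability q of an abnormal value per visit in one direction.

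With independent visits the probability is q(1 − q)^K:

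| q | K | Probability | Of 171 |
|---|---|---|---|
| 5% | 4 | 0.05 × 0.95^4 = 4.1% | 7 |
| 5% | 9 | 0.05 × 0.95^9 = 3.2% | 5 |
| 1% | 4 | 0.01 × 0.99^4 = 1.0% | 2 |
| 1% | 9 | 0.01 × 0.99^9 = 0.9% | 2 |

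Persistent abnormalities lower these numbers. In a simulation with q = 5% and a within-subject correlation of 0.7, including Week 12 raised the proportion with an abnormal extreme from 12.1% to 13.5% for K = 4 and from 17.7% to 18.5% for K = 9. The differences of 1.4 and 0.8 points correspond to about 2 and 1 of 171 subjects.

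With Week 12 assigned to the Double-Blind Period only, the contribution is zero.

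**The case against.** The strongest reply is that Section 10.3 already points to one assignment. It takes the last Double-Blind visit as Double-Blind end of treatment, and the last Double-Blind dose is at Week 8, so a sensible programmer would treat Week 12 results as Double-Blind data. That supports the proposed fix. It does not remove the problem, because nothing excludes the same result from the Dose-Blind Period.

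Second, Section 3.1 says that selected Dose-Blind tables use sequence columns such as placebo to 160 mg. If the laboratory shift tables do so, a Week 12 value stays within its own sequence and is not pooled with subjects randomized to 160 mg. This stands as a limit: the choice is left to the table shells, which are not shown. Even then the extreme would be a pre-switch value labelled Dose-Blind.

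Third, the order of blood draw and injection at Week 12 is not stated. That is so, and a pre-injection draw is an inference. A sample taken shortly after the injection on the same day would still mainly reflect the preceding 12 weeks.

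A reader might go further and infer that safety follow-up (SFU) values of early discontinuers are never post-treatment, since the SAP says "Post-treatment period: the post-treatment period (Follow-up period) is the period after the" Week 48 visit. The document does not support this. The same line equates post-treatment with follow-up, Section 2.3 sends early withdrawals into the SFU Period, and Sections 10.1 and 10.2 use a 140-day window after the last dose for time at risk and treatment-emergent events. Nor does the problem extend to vital signs and ECG, which Sections 10.5.1 and 10.5.2 summarize by visit.

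**Conclusion.** The point holds for the laboratory maximum/minimum shift tables. Followed as written, Section 3.2.2 allows a Week 12 result that reflects placebo, 16 mg or 64 mg to become a Dose-Blind worst value, and it counts that result in both periods. Up to 171 of 285 planned subjects are exposed to this.

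The effect on the tables is probably small: about 1 to 7 of 171 subjects per analyte and direction under the illustrative assumptions. The true number depends on the laboratory schedule, the abnormality rates, their persistence and dropout before Week 12, none of which is in this document.

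A reader might infer a larger count from where the numerical extreme falls. With exchangeable values that share is 1/(K + 1), or 20% for K = 4 and 10% for K = 9, hence 34 and 17 of 171. Those are not misattributed abnormalities: most such extremes would lie within the normal range, and the shift category would be the same without Week 12.

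The correction is worth making because a stated rule gives a wrong result and the remedy is simple.

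**What to change.** State in Section 3.2.2 or 10.3 that scheduled Week 12 laboratory values belong to the Double-Blind Period only. State also that the Dose-Blind maximum and minimum are taken from scheduled assessments after the first Dose-Blind injection, up to the Week 48 or early termination visit. The upper limit makes explicit for the extremes what Section 10.3 already uses for Dose-Blind end of treatment.

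The cost is one sentence in the SAP, a period flag in the laboratory analysis dataset and a rerun of any affected shift tables. No new data are needed, and the adverse event, exposure, vital sign and ECG rules stay as they are.

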#### **Definition of Baseline values** 3.3

tionsthereof The last valid measurement before first dose of study drug (Visit 2) will be used as the Baseline value. If a scheduled Baseline assessment is taken on the same day and after the first administration of study medication, it will be analyzed as the first post-Baseline assessment. If a scheduled Baseline assessment is taken on the same day as first administration of study medication and no time is collected, it will be assumed to have been taken prior to study medication.

The exception of the above rule are the questionnaires collected from the vendor ERT and measurements for C-reactive protein (CRP) and high sensitivity C-reactive protein (hs-CRP). For those measurement, the last valid measurement at the same day as Visit 2 will be used as the Baseline value.

However, for some variables, assessments may be scheduled for Screening only and not for Baseline. In this case the Screening value will be utilized as Baseline value. If a Baseline measurement is missing, and a Screening value available, the Screening value will be utilized as ation 3P Baseline instead.

#### **Protocol deviations** 3.4

Important protocol deviations are defined as those deviations from the protocol likely to have a meaningful impact on the primary efficacy outcomes for an individual subject. Important protocol deviations will be identified and classified by the deviation types defined in the appropriate protocol-specific document. All protocol deviations will be reviewed as part of the ongoing data cleaning process and all important deviations will be identified and documented prior to unblinding to confirm exclusion from Per Protocol Set (PPS), Pharmacokinetics Per-Protocol Set (PK-PPS), and Pharmacodynamics Per-Protocol Set (PD-PPS). The exclusion from PPS is limited to the Double-Blind Period, ie. only subjects with important protocol deviations prior to re-randomization at Visit 7 (Week 12) will be excluded from PPS. Subjects with important protocol deviations after Visit 7 (Week 12) will not be excluded from PPS.

### Mapping of assessments performed at early termination visit 3.5

Study assessments at an early termination visit where visit date matches the visit date of a scheduled visit will be summarized at the scheduled visit with the same visit date. Premature study termination visit assessments that do not have a scheduled visit with a matching date will be assigned to the next scheduled site visit following the last visit where assessments were available regardless whether or not there will be an assessment on this visit. The assessment of AbAb is an exception to this rule: AbAb will be mapped to the next visit where antibody levels are measured. For subjects who discontinue study treatment early and return for the Week 12 visits as per the protocol, the assessments collected at that visit are summarized as Week 12 assessments.

his do

### Randomized Set (RS) 3.6.2

The RS will consist of all randomized subjects.

#### Safety Set (SS) 3.6.3

The SS will consist of all randomized subjects who received at least 1 dose of IMP.

#### 3.6.4 Full Analysis Set (FAS)

The FAS will consist of all randomized subjects who received at least 1 dose of IMP and have a valid measurement of the primary efficacy variable at Baseline.

### Per-Protocol Set (PPS) 3.6.5

The PPS will consist of all subjects in the FAS who had no important protocol deviation affecting the primary efficacy variable. The subjects with important protocol deviations will be predefined and evaluated during a data evaluation meeting prior to unblinding of the data.

### 3.6.6 Pharmacokinetics Per-Protocol Set (PK-PPS)

The PK-PPS is a subset of the FAS, consisting of those subjects who had no important protocol deviations affecting the pharmacokinetic variables, as confirmed during ongoing data cleaning meetings prior to database lock.

inis do

#### 3.6.10 **Dose-Blind Responder Set (DBRS)**

The DBRS consists of all subjects starting the Dose-Blind Period and who received at least 1 dose of the IMP during the Dose-Blind Period and who have achieved at least a 10% reduction from Baseline in PGADA and total and nocturnal spinal pain at Week 16, Week 24, and Week 36.

#### Corrected Escape Subject Set (cESS) 3.6.11

The cESS is a corrected version of the ESS, which was incorrectly defined previously. The cESS consists of subjects that have shown less than a 10% improvement in SJC and TJC at either Week 16, Week 24, or Week 36 and received rescue therapy.

#### Corrected Dose-Blind Responder Set (cDBRS) 3.6.12

The cDBRS is a corrected version of the DBRS, which was incorrectly defined previously. The cDBRS consists of subjects that have shown at least a 10% improvement in SJC or TJC at Week 16, Week 24 and Week 36. Subjects that would be in the cESS, including subjects that discontinue, that did not receive rescue therapy will be in the cDBRS.

#### 3.8 Center pooling strategy

Centers will be pooled into geographic regions for analysis purposes. Centers will be grouped in the geographic regions North America, Western and Eastern Europe.

#### 3.9 **Coding dictionaries**

Medical history and AEs will be coded using the Medical Dictionary for Regulatory Activities (MedDRA) version 19.0. Previous and ongoing medical history will be classified by primary system organ class and preferred term (PT).

All AEs will be classified by primary system organ class, high level term and PT. Prior and concomitant medications will be coded using version SEP2015 of the World Health Organization Drug Dictionary (WHO-DD) and will be classified by Anatomical Main Group, Pharmacological Subgroup, and PT. Medical procedures will not be coded.

#### 3.10 Changes to protocol-defined analyses

Instead of stopping the pairwise testing of each bimekizumab dose versus placebo once it failed to reach significance at a significance level of  $\alpha = 0.05$ , the pairwise testing will continue and further pairwise comparisons are seen as non-significant.

No fixed sequence testing will be used for the secondary efficacy variables.

Time to a given response is defined as the length in weeks from Baseline until the first date when the response is achieved. In the definition the length was changed from days to weeks due to easier interpretation.

## STATISTICAL/ANALYTICAL ISSUES

## Adjustments for covariates

The primary efficacy analysis and secondary analysis will be adjusted for treatment, geographic hisdocul region, and prior TNF inhibitor exposure (yes/no).

Note: The imputation model based on the MCMC method will only allow continuous variables as predictors. Therefore, prior TNF inhibitor exposure and geographic region will be re-coded as numeric variables (with values of 0 or for the levels of TNF [1=prior inhibitor exposure, 0=non prior inhibitor exposure] and two binary variables for geographic region [Variable 1:1=North America, 0=others, Variable 2: 1=Eastern Europe, 0=others] as representation of geographic region).

Note: To avoid that imputed values are outside of the pre-defined range of values for the ASAS components (eg. PGADA [0-10]) maximum and minimum values for imputed variable values are specified. Moreover, the rounding options for imputed values are used where appropriate.

Once the intermediate missing data are imputed, the monotone missing data will be imputed for all patients with monotone regression including geographic region, and prior TNF inhibitor exposure as covariates. The dataset is the output dataset of the partial imputation. Since this dataset already has 100 imputed values at each visit, only one imputation will be performed.

Note: Maximum and minimum values (and rounding where appropriate) are specified for imputed variable values to avoid values outside of the pre-defined range of values.

This docurger The ASAS40 response will be calculated using the complete datasets. That is, the values of the ASAS components at Week 12 based on the complete datasets will be compared to their corresponding Baseline values to calculate an ASAS40 response for each subject (as described in Section 8.1.1). Each complete data set will then be analyzed based on a logistic regression model with factors of treatment group, geographic region, and prior TNF inhibitor exposure.

(1)

3. The Week 12 results from the logistic regression analysis of each of the 100 imputed data sets will be combined for overall inference using Rubin's rules, which account for the uncertainty associated with the imputed values (Rubin, 1987).

As the estimates of the odds ratios from the logistic regression model in step 3 follow a lognormal distribution, a log transformation is needed to normalize these estimates since the procedures for combining results from multiple imputed datasets are based on the assumption that the statistics estimated from each imputed dataset are normally distributed. Therefore the log of the odds ratio estimates from the logistic regression model are single inference (step 3). Additionally the statistics are fall. transformed as follows:

$$SE = \frac{\log(UCL) - \log(LCL)}{2Z_{\alpha/2}}$$

where UCL and LCL are the upper and lower confidence limit, respectively, for the confidence interval of the odds ratio from the logistic regression model, and  $Z_{\alpha/2}$  is the relevant critical value from the standard normal distribution (1.96 for a 95% confidence interval). The estimates of the log odds ratio for each bimekizumab dose relative to placebo and the corresponding upper and lower confidence limits will be provided. The odds ratio is estimated by exponentiating the estimate of the log odds ratio. The confidence limits of the odds ratio are then estimated as follows:

$$LCL = QR * \exp(-SE * Z_{\alpha/2})$$

$$UCL = OR * \exp(SE * Z_{\alpha/2})$$
(3)

where OR is the back-transformed estimate of the odds ratio just described, SE is the standard error of the log odds ratio and  $Z\alpha/2$  is the relevant critical value from the standard normal distribution (1.96 for a 95% confidence interval). These calculations will be done such that odds ratios and corresponding confidence intervals are calculated for the odds ratio of each bimekizumab dose versus placebo. Note that the p-values presented in the tables are not impacted by the transformations described above.

The supportive analysis number 3 (analysis of the ASAS components), and all continuous secondary efficacy variables will use the same multiple imputation method as described above. Instead of using the logistic regression model the ANCOVA with treatment group, geographic region, and TNF inhibitor exposure as fixed effects and the Baseline values as covariate will be used. No log transformation is needed for the ANCOVA estimations.

Following Rubin (1987), multiple imputation estimates of descriptive statistics are computed by simply averaging the estimates from m = 1, ..., M independent repetitions of the imputation algorithm:

thereof

(4)

$$\bar{\theta} = \frac{1}{M} \sum_{m=1}^{M} \hat{\theta}_m$$

where  $\hat{\theta}_m$  is the estimate of  $\theta$  from the completed data set m = 1, ..., M (Berglund, 2014).

The imputation model will be applied for each treatment group separately. However, in the event there are computational challenges with the imputation model (eg, due to a standard deviation of 0 for responses of a given imputation), it is acceptable to modify the imputation model to include treatment as a variable in the model rather than running a separate model for each treatment group. It should be noted that doing so assumes that treatment does not interact with any of the other variables in the imputation model.

